5.2. General Methods

In general, for descriptive analyses, number and percent will be presented for binary endpoints. Number, median, Q1 and Q3 will be presented for descriptive analyses of continuous efficacy endpoints.

5.2.1. Analysis of Primary Endpoint

The population for the primary analysis will be all participants in the FAS having valid biomarker data at baseline and Week 12.

The primary endpoints in this study include mean fold-changes for the following biomarkers:

- General inflammation (MMP12);
- Hyperplasia (K16);
- Th2 (CCL17, CCL18, CCL26);
- Th22 (S100A8, S100A9, S100A12).

In each participant, expression levels from RT-PCR will be normalized to the housekeeping gene RPLP0 (validated in other studies) by negatively transforming the Ct values to $-dCt$, obtaining an equivalent to log2 scale expression values (reporting unit: log2 [Expression/RPLP0]). The expression values below detection will be estimated for each gene as the 20% of the minimum of unlogged values across all samples (which is equivalent to subtracting 2.321928 from the $-dCt$ minimum value). The expression levels below detection may provide important information about some markers that significantly change with treatment (eg, the expression may decrease below the level of detection after treatment), therefore this imputation is an important step in the analysis.

RT-PCR expression data in log2 scale will be modeled using a mixed effect model with Treatment, Time Point, and Tissue Type as a fixed effect and a random intercept for each participant. This model will yield unbiased estimates and valid inferences in the presence of a missing data mechanism that is missing at random (MAR).¹ This approach introduces less bias than restricting the analysis for participants with complete observations. Contrasts will be used to estimate the log2 fold-changes for each treatment group. Fold-changes will be computed by obtaining the antilog of log2 fold-changes. Point estimates and 95% confidence intervals (CIs) will be obtained for the fold-change from baseline in the biomarker values for each treatment group based on this model.

Correlation analyses will be performed to assess if the fold-change from baseline in biomarkers correlates with change (from baseline) in the clinical efficacy endpoints such as IGA, EASI, and Peak Pruritus NRS.

Supportive analyses for the primary endpoint will also be performed using the PPAS.

While statistical tests of hypotheses will not be performed to compare the fold-change from baseline in the PF-04965842 groups versus placebo, the point estimates and 95% CIs for the two PF-04965842 dose groups will be assessed in relation to those from the placebo group. A fold-change from baseline observed in the PF-04965842 groups alone (and correlated with efficacy) but not in the placebo group is likely due to the mechanism of action of PF-04965842.

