The double-blind treatment period will last from Baseline/Day 1 to Week 12. For all participants, one 4.5 mm skin biopsy (punch biopsy) will be collected from each target treatment area at the specified time points. Lesional skin biopsies will be collected at Baseline/Day 1 (Week 0), Day 29 (Week 4), and Day 85 (Week 12), with an optional lesional skin biopsy collection at Day 15 (Week 2). A non-lesional skin biopsy will be collected at Baseline/Day 1 (Week 0), with an optional non-lesional skin biopsy collection at Day 85 (Week 12). **CCI**

Biopsy samples will be used to perform gene expression by quantitative reverse transcriptase polymerase chain reaction (qRT-PCR), including Taqman Low Density Array (TLDA) PCR, for 48 genes including 2 housekeeping genes (18S and RPLP0), as well as single gene PCR for a few genes that are below detection level on TLDA (see [Table 1](#)). **CC1**

Immunohistochemistry (IHC) analysis will be performed for cellular infiltrates, Keratin 16 (K16) staining, and hematoxylin and eosin (H&E) staining.

Many of the genes to be analyzed in this study are considered key biomarkers associated with AD pathways. For this study, the following biomarkers were selected for the primary endpoint: general inflammation (MMP12), hyperplasia (K16), Th2 immune response (CCL17, CCL18, CCL26), and Th22 immune response (S100A8, S100A9, S100A12).

CC1

The efficacy outcomes (eg, IGA, EASI, % body surface area [%BSA], and peak pruritus numerical rating scale [PP-NRS]) are collected so that any associations between biomarker changes and these efficacy outcomes may be evaluated. The clinical improvement will be correlated with the suppression of individual immune pathways, cellular infiltrates, and changes in epidermal biomarkers. Differences between groups and changes from baseline will be estimated. Tests of hypotheses for differences between treatment groups will not be performed.

Safety will be assessed by physical exams, standard laboratory testing, and collection of AEs.

Refer to the [Schedule of Activities](#) for a complete list of assessments to be performed during the study.

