9. STATISTICAL CONSIDERATIONS

9.1. Estimands and Statistical Hypotheses

9.1.1. Estimands

The primary objective of this study is to assess the effects of abrocitinib on lesional and non-lesional skin biomarkers of adult participants with moderate-to-severe AD. The following estimand attributes will be considered:

- Population: Participants with moderate-to-severe AD as defined by the inclusion criteria;
- Variable: Fold-change from baseline in the biomarkers for general inflammation (MMP12), hyperplasia (K16), Th2 immune response (CCL17, CCL18, CCL26), and Th22 immune response (S100A8, S100A9, S100A12);
- Intercurrent event: All data collected will be utilized;
- Participants need to have a baseline and week 12 assessment to be included in the analysis.
- Population-level summary: Mean fold-change from baseline within each treatment group.

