9.4.1. Analysis of the Primary Endpoint

The population for the primary analysis will be all participants in the FAS having valid biomarker data at baseline and Week 12.

The primary endpoints in this study include mean fold-changes for the following biomarkers:

- General inflammation (MMP12);
- Hyperplasia (K16);

- Th2 (CCL17, CCL18, CCL26);
- Th22 (S100A8, S100A9, S100A12).

In each participant, expression levels from RT-PCR will be normalized to the housekeeping gene RPLP0 (validated in other studies) by negatively transforming the Ct values to $-dCt$, obtaining an equivalent to log2 scale expression values (reporting unit: log2 [Expression/RPLP0]). The expression values below detection will be estimated for each gene as the 20% of the minimum of unlogged values across all samples (which is equivalent to subtracting 2.321928 from the $-dCt$ minimum value). The expression levels below detection may provide important information about some markers that significantly change with treatment (eg, the expression may decrease below the level of detection after treatment), therefore this imputation is an important step in the analysis.

RT-PCR expression data in log2 scale will be modeled using a mixed effect model with Treatment, Time Point, and Tissue Type as a fixed effect and a random intercept for each participant. This model will yield unbiased estimates and valid inferences in the presence of a missing data mechanism that is missing at random (MAR). ²⁹ This approach introduces less bias than restricting the analysis for participants with complete observations and is consistent with estimation of a hypothetical estimand. Contrasts will be used to estimate the log2 fold-changes for each treatment group. Fold-changes will be computed by obtaining the antilog of log2 fold-changes. Point estimates and 95% confidence intervals (CIs) will be obtained for the fold-change from baseline in the biomarker values for each treatment group based on this model.

Correlation analyses will be performed to assess if the fold-change from baseline in biomarkers correlates with change (from baseline) in the clinical efficacy endpoints such as IGA, EASI, and Peak Pruritus NRS.

Supportive analyses for the primary endpoint will also be performed using the PPAS.

[figure not shown]

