5.1.1. Estimands

The primary objective of this study is to assess the effects of PF-04965842 on lesional and non-lesional skin biomarkers of adult participants with moderate-to-severe AD. A hypothetical estimand will be used for estimation. The following estimand attributes will be considered:

- Population: Participants with moderate-to-severe AD as defined by the inclusion criteria and with a valid baseline and Week 12 assessment;

- Variable: Fold-change from baseline in the biomarkers for general inflammation (MMP12), hyperplasia (K16), Th2 immune response (CCL17, CCL18, CCL26), and Th22 immune response (S100A8, S100A9, S100A12);
- Intercurrent event: All data collected will be utilized;
- Population-level summary: Mean fold-change from baseline within each treatment group.

Some secondary objectives require analyses of binary endpoints for which, a composite estimand with the following attributes will be considered:

- Population: Participants with moderate-to-severe AD as defined by the inclusion criteria and with a valid baseline;
- Variable: Binary outcome measures such as responder-based endpoints. Participants who discontinue from the study treatment for any reason are defined as non-responders after that point;
- Intercurrent event: The intercurrent event is captured through the variable definition;
- Population-level summary: Proportion of participants who are responders in each treatment group and differences in proportions of responders between each active dose and placebo.

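### The primary biomarker analysis drops participants without Week 12 data before fitting, yet is justified as unbiased under MAR and better than a complete-observation analysis

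*SAP*

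**What the plan says.** **Who is analysed.** SAP 5.2.1 and protocol 9.4.1 carry the same rule: "The population for the primary analysis will be all participants in the FAS having valid biomarker data at baseline and Week 12". Protocol 9.1.1 repeats it within the estimand: "Participants need to have a baseline and week 12 assessment to be included in the analysis". SAP 5.1.1 defines the estimand population as participants "with a valid baseline and Week 12 assessment", next to the attribute "Intercurrent event: All data collected will be utilized". SAP Table 1 shows that the Week 12 condition was added deliberately in version 2. SAP 6.1.1 nevertheless lists the population as the FAS, with no condition.

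**How the model is justified.** SAP 5.2.1 says the random-intercept mixed model is unbiased under MAR, and then: "This approach introduces less bias than restricting the analysis for participants with complete observations". Protocol 9.4.1 has the same sentence with a clause tying it to a hypothetical estimand. SAP Table 1 records that references to a hypothetical estimand were removed, but SAP 5.1.1 still reads "A hypothetical estimand will be used for estimation".

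**What else is planned.** Supportive analysis of the primary endpoint uses the PPAS, which SAP 4.2 limits to participants with valid biopsies at baseline and on schedule. SAP 5.2.1 then reads the group estimates against placebo to attribute changes to the mechanism of action.

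**The concern.** A likelihood-based mixed model earns its MAR property by keeping incomplete participants' observed samples in the likelihood. Protocol 4.1 requires lesional biopsies at Weeks 0, 4 and 12, so someone lost after Week 4 has two usable samples. The entry rule discards both. For that person the plan applies the kind of restriction it says it improves on.

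If loss of Week 12 data is related to baseline expression or to early change, the Week 12 estimate moves away from what an all-FAS analysis would give. If loss also differs between arms, so does the reading against placebo on which the mechanistic conclusion rests. No planned analysis is named that would show this.

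**Working it through.** **1. The plan's precision figure.** Inputs (SAP 2.2, protocol 9.2): n = 17 per arm, SD = 5, target half-width w = 3.2, 95% CI, chi-square sample variance.

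P(half-width ≤ w) = P(χ²(n−1) ≤ (n−1)·[w√n / (t·SD)]²)

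With t(0.975, 16) = 2.120 the bound is 16·[3.2·√17 / (2.120·5)]² = 24.79, giving 92.6%. The stated figure of about 92% is reproduced. It makes no allowance for exclusions: at 16, 15, 14 and 13 analysed per arm the formula gives 88.2%, 82.3%, 74.9% and 66.4%.

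**2. What the restriction does.** Once everyone retained has both baseline and Week 12, the Week 12 contrast is a completer contrast. In a one-arm simulation (400,000 participants, true log2 change −2, intercept and residual SD 1, loss driven by poorer Week 4 change at 1.5 log-odds per SD), the restricted model equalled the raw completer mean:

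| Loss | All samples | Restricted | Completer mean |
|---|---|---|---|
| 10% | −2.002 | −2.088 | −2.088 |
| 20% | −1.994 | −2.155 | −2.155 |
| 30% | −1.997 | −2.228 | −2.228 |

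**3. Size under stated assumptions.** Assume log2 SD σ = 1.5, equal correlation ρ = 0.5, one arm, lesional tissue. Let z be the standardised driver of loss, with logistic slope b per SD, and m the mean of z among those retained. The bias is Cov(Week 12 − baseline, driver) / SD(driver) × m:

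- Week 4 change as driver: σ√((1−ρ)/2)·m = 0.75m. Here m is negative, since poor responders leave, so bias is negative.
- Baseline as driver: −(1−ρ)σ·m = −0.75m. Same size, positive.
- Week 4 level alone: (ρσ² − ρσ²)/σ·m = 0.

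m = −E[z·P(loss)] / (1 − loss rate). At 30% loss m is −0.143, −0.253 and −0.327 for b = 0.5, 1.0 and 1.5. Absolute bias, 0.75·|m|:

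| b | 5% | 10% | 20% | 30% |
|---|---|---|---|---|
| 0.5 | 0.02 | 0.04 | 0.07 | 0.11 |
| 1.0 | 0.04 | 0.07 | 0.13 | 0.19 |
| 1.5 | 0.05 | 0.09 | 0.17 | 0.25 |

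Simulations of 400,000 participants per scenario agree. At 30% loss the fold-change is multiplied by 2^(∓0.107) = 0.93 to 1.08 at b = 0.5, and by 2^(∓0.245) = 0.84 to 1.19 at b = 1.5.

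**4. Against placebo.** Equal loss by the same mechanism gives 0. With 10% loss in one arm and 30% in the other, the difference is 0.107 − 0.037 = 0.07, 0.190 − 0.068 = 0.12, and 0.245 − 0.091 = 0.15.

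**5. Does using all samples repair it?** Under equal correlation the all-sample random-intercept fit stays within about 0.007 of the truth. If correlation decays (0.5 between adjacent visits, 0.25 from baseline to Week 12), then at 30% loss and b = 0.5/1.0/1.5:

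- restricted set: off by 0.16/0.28/0.37
- all-sample random intercept: off by up to 0.05/0.10/0.12
- all-sample unstructured covariance: off by at most 0.005

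With tissue type added at 20% loss, the all-sample lesional contrast is within 0.003 (cross-tissue correlation 0.5) or 0.04 (0.25), against 0.07 to 0.18 when restricted. At 0.25 the non-lesional contrast is off by up to 0.07 in either set. These fits use separate visit and tissue means per arm, which SAP 5.2.1 does not spell out.

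**6. At 17 per arm.** With 20% loss, bias of 0.07/0.13/0.17 compares with a sampling SD of about 0.40, and 95% CI coverage is 94.8/94.0/93.3%. At 30% loss, coverage is 94.7/93.2/91.6%. Precision is similar either way (at 20% loss, SD 0.39–0.41 on all samples, 0.41–0.42 restricted), so the issue is bias rather than lost precision.

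**7. Two open definitions.** The documents do not say which tissue must be valid at Week 12, and the non-lesional biopsy then is optional. If both were needed, 20/40/60% declining would leave 17 × 0.8/0.6/0.4 = 13.6/10.2/6.8 per arm before other loss. Nor is it clear whether an early-termination biopsy counts: Visit 10 is labelled as both end of treatment and early termination, while SAP Appendix 2 sets Week 12 at Days 72 to 99 without naming biomarkers.

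**The case against.** The strongest reply is that the analysis matches its own target: the Week 12 condition was added on purpose and is part of the SAP estimand population. The bias figures are all relative to an all-FAS target that the plan does not adopt. That stands, so the charge is not that the wrong set is analysed. But the condition is a post-randomisation event, and matching a restricted population does not make the written justification true of those excluded.

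Second, complete observations can be read as every scheduled sample. On that reading the sentence is true of the retained set, where Week 4 and optional biopsies may be missing. This too stands. The fault is that the sentence is unqualified, while the gap most relevant to a Week 12 estimate is handled by exclusion. The attribute on using all collected data may likewise concern only data after intercurrent events, so it is weaker evidence of conflict.

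Third, the size rests on assumptions, is below the sampling SD, and can be zero; there are no hypothesis tests. All correct. If early-termination biopsies count as Week 12, exposure is small. Lesional-only entry is the more natural reading, because the sample size is framed on skin lesions, so the small counts in step 7 are an unlikely extreme.

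Fourth, other analyses may cover the gap. SAP 5.2.2 visibly lists five of the eight primary genes (S100A8, S100A9, S100A12, CCL18, CCL26) under an MAR mixed model, SAP 6.2.1 uses the FAS, and a secondary endpoint covers lesional gene expression over time. None states a Week 12 condition. However, these sections are partly redacted, the visible entries in SAP 6.2 are epidermal thickness, Ki-67 and K16, and none is named as a check on the primary result.

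**Conclusion.** The concern holds. The plan credits its primary analysis with a property it lacks for participants without the required Week 12 data, and its one named supportive analysis cannot show the consequence. Confidence in that mismatch is high.

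Whether it causes material bias is unknown. Under the assumptions in step 3 the shift ranges from 0 to 0.25 log2 at up to 30% loss. Varying the correlation from 0.3 to 0.7 at 30% loss gives about 0.06 to 0.15 at b = 0.5 (0.45 × 0.143 to 1.05 × 0.143) and 0.15 to 0.34 at b = 1.5 (0.45 × 0.327 to 1.05 × 0.327), when baseline drives loss. It is zero against placebo with equal loss and mechanism. In an estimation-only study of this size, this should be fixed but does not invalidate the trial.

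**What to change.** **Preferred.** Delete the Week 12 requirement from SAP 5.1.1 and 5.2.1 and protocol 9.1.1 and 9.4.1. Fit the mixed model to all FAS participants with any valid biomarker sample, with the Week 12 contrast by treatment group and tissue type. Report the baseline-plus-Week-12 set as a sensitivity analysis. Check the random-intercept covariance against a less restrictive structure, since step 5 shows it can leave residual bias. Assign early-termination biopsies to a time point by actual study day.

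**If the restriction stays primary.** Add the all-FAS mixed model as a sensitivity analysis, name the tissue that defines entry, and say that the estimand covers only participants with a valid Week 12 biopsy. Limit the MAR and bias statements to biopsies not needed for entry.

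**Either way.** Remove the leftover hypothetical-estimand wording in SAP 5.1.1 and protocol 9.4.1, and align the population in SAP 6.1.1 with the set used.

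**Cost.** Text changes in those sections and one extra table; no new data. Dropping the condition changes the estimand population, and SAP section 2 says major changes to the primary analysis are also reflected in a protocol amendment, so one is needed. The downside is some reliance on the model for participants without Week 12 data.

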While statistical tests of hypotheses will not be performed to compare the fold-change from baseline in the abrocitinib groups versus placebo, the point estimates and 95% CIs for the two abrocitinib dose groups will be assessed in relation to those from the placebo group. A fold-change from baseline observed in the abrocitinib groups alone (and correlated with efficacy) but not in the placebo group is likely due to the mechanism of action of abrocitinib.

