6.1.1. Primary Analysis

- Summary: Fold-change from baseline at Week 12;
- Population: FAS;
- Statistical Method: Estimate and 95% CI from MMRM described in [Section 5.2.1](#);
- Missing Data: No explicit imputation.

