6.6. Subset Analyses

Summary statistics for co-primary endpoints will be presented by subgroups below.

- Age (years) group; (<40 , ≥ 40);

- Race (White, Black or African-American, Asian, Other¹);
- Baseline disease severity (moderate, severe).

Point estimates and 95% confidence intervals will be derived from MMRM models as described in [Section 5.2.1](#).

The primary purpose of the subgroup analyses is to check for consistency of results across subgroups, to make sure overall results are not being driven by some subset of subjects.

Graphical display (eg, forest plots) of the differences between treatment groups will be presented. There is no intention to have any specific inference within subgroups.

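### The primary biomarker model has no treatment-by-time term, so it cannot give the per-arm fold-changes it promises, and the primary analysis specifies no dose-versus-placebo estimate

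*SAP*

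**What the plan says.** SAP 5.2.1 describes the RT-PCR data, taken as log2 values, as "modeled using a mixed effect model with Treatment, Time Point, and Tissue Type as a fixed effect and a random intercept for each participant". Protocol 9.4.1 uses the same words. Both then state: "Contrasts will be used to estimate the log2 fold-changes for each treatment group". Point estimates and 95% CIs for each arm's fold-change are to come from this model. SAP 6.1.1 adds nothing to the specification; its method is "Estimate and 95% CI from MMRM described in" SAP 5.2.1.

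The estimand in SAP 5.1.1 is within-arm: "Population-level summary: Mean fold-change from baseline within each treatment group". Protocol 9.1.1 agrees. Placebo enters through a side-by-side reading; in protocol 9.4.1, "the point estimates and 95% CIs for the two abrocitinib dose groups will be assessed in relation to those from the placebo group". The SAP then attributes one pattern of results to the drug's mechanism of action: "A fold-change from baseline observed in the PF-04965842 groups alone (and correlated with efficacy) but not in the placebo group is likely due".

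Two other places expect group differences. Protocol 4.1 says "Differences between groups and changes from baseline will be estimated", and separately rules out hypothesis tests between groups. SAP 6.6 cites the SAP 5.2.1 model and says that a graphical display "of the differences between treatment groups will be presented".

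**The concern.** There are two linked gaps.

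**The model.** With main effects only, the arms may differ in level but not in change over time. The listed terms therefore contradict the output promised in the same paragraph, and the fitted model is not pre-specified.

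**The comparison.** The scientific question is how far the change on each dose exceeds the change on placebo. No estimate or CI for that quantity is specified for any of the eight primary biomarkers. Finding a change in one arm and not in another does not measure how far the arms differ, and the plan does not define what counts as an observed change. The reading can fail both ways. Equal true changes can look different by chance, and a large drug effect can fail the condition because placebo also moved detectably.

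At stake are the primary estimates, which depend on terms chosen after the SAP is final, and the basis for the mechanism-of-action conclusion.

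**Working it through.** **1. The plan's own precision figure.** Inputs from protocol 9.2: n = 17 per arm, SD 5, half-width 3.2, 95% CI.
- Expected-size half-width: t(0.975, 16) × 5/√17 = 2.120 × 1.213 = 2.57.
- Chance of 3.2 or less: P(chi-square on 16 df ≤ 16 × (3.2 × √17/2.120)²/25) = 92.6%. This reproduces the stated figure of about 92%.

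**2. What the listed model estimates.** Write the mean as intercept + arm + time + tissue, plus a participant intercept. For any arm and tissue, Week 12 minus baseline is time(W12) − time(W0); the arm, tissue and participant terms cancel. With 3 arms, 4 biopsy visits and 2 tissues the model has 1 + 2 + 3 + 1 = 7 fixed-effect parameters, and this contrast is the same vector for all 3 × 2 arm-tissue combinations.

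This was confirmed in 40 simulated trials of 17 per arm. The true lesional log2 changes were assumed, not taken from the documents. Non-lesional changes were set at one fifth of these, and half of participants had the optional Week 12 non-lesional biopsy.

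| Model | Placebo | 100 mg | 200 mg |
|---|---|---|---|
| Assumed lesional truth | −0.3 | −1.5 | −3.0 |
| As listed | −1.09 | −1.09 | −1.09 |
| Treatment-by-time, tissue main effect only | −0.12 | −1.01 | −2.16 |
| Treatment-by-time, lesional samples only | −0.27 | −1.49 | −3.05 |

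So adding treatment-by-time is not sufficient; the handling of tissue also moves the answer. A full three-way model is not a safe default. It has 3 × 4 × 2 = 24 cells, but non-lesional skin is not sampled at Weeks 2 or 4, so 3 × 2 = 6 cells are empty and 18 remain.

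**3. What the side-by-side reading does.** The documents give no log2 SD and no expected placebo change, so this is illustrative. Assumptions: *observed* means that a 95% t CI excludes no change; the efficacy-correlation condition is ignored; n = 17 per arm; the true change is identical in all arms. Let p be the chance that one arm's CI excludes no change (noncentral t, 16 df).

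| Common change (SD units) | p | Both doses, not placebo: p²(1−p) | One given dose, not placebo: p(1−p) |
|---|---|---|---|
| 0 | 0.050 | 0.2% | 4.8% |
| 0.25 | 0.163 | 2.2% | 13.6% |
| 0.5 | 0.491 | 12.3% | 25.0% |
| 0.6 | 0.642 | 14.8% | 23.0% |
| 0.75 | 0.827 | 11.8% | 14.3% |
| 1.0 | 0.972 | 2.7% | 2.8% |

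The maximum for both doses is 14.8%, at 0.615 SD. In 100,000 simulated trials a direct dose-minus-placebo contrast with pooled SD excluded no difference in 5.0% per dose and 1.0% for both, whatever the common change.

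**4. Precision of a direct contrast.** On the protocol's scale, with SD 5 in each arm:
- Half-width: t(0.975, 32) × 5 × √(2/17) = 3.49, against 2.57 within arm.
- Chance of 3.2 or less: 27.5%, against 92.6%.

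On the log2 scale, for an assumed SD of change of 1 to 3, the 95% CI is the estimate times or divided by 1.43 to 2.91 within arm, and 1.62 to 4.28 for the dose-to-placebo ratio.

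**The case against.** **The interaction was plainly intended.** The factors may be named as shorthand, per-arm contrasts are promised from the model, and SAP 6.1.1 calls it an MMRM. This is probably right, and it settles that some treatment-by-time term was meant. It does not settle the tissue terms, and the table above shows that these change the primary estimates.

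**Within-arm estimation is a deliberate choice.** The estimand, the sample size and the absence of tests all agree. The sentence in protocol 4.1 names no endpoint and is partly met by the planned dose-placebo differences in clinical outcomes (SAP 5.2.3, 6.3.1 and 6.3.4). A reader could also approximate the ratio from the reported per-arm CIs. All of this is fair. But protocol 4.1 separates estimating from testing, and the gap falls on the primary endpoint of a placebo-controlled study, where the plan goes on to attribute mechanism by comparing arms.

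**The 14.8% depends on how the attribution sentence is read.** The plan defines no rule, requires correlation with efficacy, and says the CIs will be assessed against placebo. If both dose CIs must also lie clear of the placebo CI, the same null gives under 0.1%. This stands: the figure shows the risk under one plausible reading of an undefined term and is not the trial's error rate.

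**SAP 6.6 is ambiguous.** It refers to co-primary endpoints, a label that SAP Appendix 1 applies to Week 12 IGA and EASI-75. It does cite the SAP 5.2.1 model, but it is supporting evidence only.

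**Conclusion.** Both parts hold. The contradiction between the listed terms and the promised per-arm output is exact and needs no assumption: as written, the fold-change is identical in every arm. That the primary analysis lacks a dose-versus-placebo estimate is also clear from the text.

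The size of the second problem is illustrative. Under the stated reading and equal true changes, both doses but not placebo show a change in 0.2% to 14.8% of trials, depending on the common change, against 1.0% for a direct contrast on both doses. This should be fixed before the database is locked. It is a defect of specification and inference; the design and data collection can support the right analysis.

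**What to change.** 1. In SAP 5.2.1 and protocol 9.4.1, name the treatment-by-time terms. Add tissue interactions only for sampled combinations: lesional at baseline, Week 2 (optional), Week 4 and Week 12; non-lesional at baseline and Week 12 (optional).
2. For each of the eight primary biomarkers, report from that model the ratio of Week 12 lesional fold-changes, each dose versus placebo, with a 95% CI and no test, beside the within-arm fold-changes. Lesional skin leads because the sample size is based on it and the Week 12 non-lesional biopsy is optional; say so, since the primary objective covers both tissues.
3. Reword the attribution sentence to rest on the size and CI of the ratio, with correlation to efficacy as support.
4. Add the ratio to the population-level summary in SAP 5.1.1 and protocol 9.1.1, and to SAP 6.1.1, to match protocol 4.1.
5. State that the sample size was set for within-arm precision and that the ratio is less precise.

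Optionally, constrain baseline means to be equal across arms. The variance factor is (1 + rho)/2; at an assumed rho of 0.4 this is 0.70, and √0.70 = 0.84, so the contrast's half-width falls by 16%.

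**Cost.** No new patients, samples or tests. There are two extra contrasts per biomarker, and fixed-effect parameters rise from 7 to at most 18. Changing the protocol sections means an amendment with IRB/IEC approval (SAP 2; protocol 10.1.1). The main statistical price is the wider interval shown in step 4 of the working, and reporting it makes that uncertainty visible.
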